4.2. Safety Analysis Set

The safety analysis set (SAS) will include all participants who are randomized and receive at least one dose of the study treatment (ie, etrasimod or placebo). Participants will be analyzed in the treatment groups as they receive. If a participant is treated but not randomized, then the participant will be excluded from SAS. A narrative will be provided for this participant in the CSR. The SAS will be the analysis set for safety analyses in all phases of the study.

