9.2. Analysis Sets

For purposes of analysis, the following analysis sets are defined:

Participant Analysis Set	Description
Full analysis set	All participants randomly assigned to study intervention, irrespective of whether they received any dose of study intervention. Participants will be analyzed in the treatment groups as they are randomized.
Safety analysis set	All participants randomly assigned to study intervention and who take at least 1 dose of study intervention. Participants will be analyzed according to the product they actually received.

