If the IA results in a decision to proceed to Part 2 of the study, approximately 340 additional (de novo) participants will be enrolled to receive etrasimod 2 mg orally, once daily, for 52 weeks in an open-label manner in order to fulfill the safety database requirements. Enrollment into Part 2 will not begin until the IA data from Part 1 DB are reviewed, and determination made as to the favorable benefit/risk of etrasimod 2 mg QD in this new target

population. Non-responders, ie, participants not achieving at least EASI-50 will be discontinued at Week 16, Part 2. The participant population in both Part 1 and Part 2 will include at least 40% of participants with moderate AD (IGA score of 3) and at least 40% of participants with severe AD (IGA score of 4). Figure 1 below provides a schematic of this study design.

The application of topical emollients/moisturizers (including those containing ceramide, hyaluronic acid, or urea) will be required at least once daily for at least 1 week prior to baseline (Day 1) and throughout the treatment period without change (ie, type, frequency, application). TCS and other medicated topical treatments for AD must be discontinued at least 1 week prior to baseline (Day 1) and are not permitted in the double-blind treatment period. Safety follow-up visits will occur at 2 and 4 weeks after the last dose of study treatment. Medicated and non-medicated rescue medications are not permitted during the Part 1 DB portion. For Part 1 OLE and Part 2 medicated and non-medicated topical treatments for AD will be permitted at the discretion of the investigator and in accordance with their usual practice.

Figure 1. Study Schematic

PART 1 (N=60) DOUBLE-BLIND EFFICACY AND SAFETY STUDY WITH A 52-WEEK OPEN-LABEL EXTENSION

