4.1. Full Analysis Sets

The full analysis set (FAS) will include all participants who are randomized to the study irrespective of whether they receive any dose of study intervention (ie, etrasimod or placebo). Participants will be analyzed in the treatment groups as they are randomized. If a participant DMB02-GSOP-RF02 7.0 Statistical Analysis Plan Template 31-Jan-2022

is treated but not randomized, then this participant will be excluded from the FAS. A narrative will be provided for this participant in the clinical study report (CSR). For a participant who is randomized but not treated, for Part 1 DB and OLE, baseline value for efficacy and safety endpoints is defined as the value obtained on the date of randomization as Day 1 or prior (if the Day 1 value is not available) in the Part 1 DB phase in the analyses.

In general, the analysis population for analyzing all efficacy endpoints in this study is defined by the complete FAS. However, there are some exceptions: some efficacy endpoints, defined by specific point reduction from baseline, require the inclusion of only participants who meet a baseline threshold in the analysis set to allow them the potential to respond in these efficacy endpoints. The details of these exceptions are provided below. Therefore, when considering analyzing an efficacy endpoint under an estimand, it is important to consider these exceptions.

FAS for Specific Efficacy Endpoints

The following four binary efficacy endpoints will only be analyzed including participants who meet the specific baseline threshold. This is to ensure that only participants with the potential to respond at a post-baseline visit are included in the analyses.

- IGA response defined as clear (0) or almost clear (1) on a 5-point scale and a reduction of ≥2 points from baseline (Appendix 2.2.1): Only participants with baseline IGA ≥2 in the FAS are included in all analyses of IGA response, knowing that only participants with baseline IGA ≥3 are eligible to enroll in this study.
- ≥4-point reduction in PP-NRS score from baseline (Appendix 2.2.4): Only participants with baseline PP-NRS ≥4 in the FAS are included in all analyses of this endpoint.
- ≥4-point reduction in Skin Pain NRS score from baseline (Appendix 2.2.5): Only participants with baseline Skin Pain NRS ≥4 in the FAS are included in all analyses of this endpoint.

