In Part 1 OLE phase, since no estimands are defined for (binary or continuous) efficacy endpoints, all observed data collected/assessed regardless of any prior intercurrent events will be included in deriving the efficacy endpoints at a visit. If the binary efficacy endpoint at any visit has missing value, it will be handled by setting the binary efficacy endpoint to non-response. This method of handling missing binary efficacy endpoint is known as missing response as non-response (MR=NR), which is similar to using Estimand E1a (treatment policy estimand). If the continuous efficacy endpoint at any visit has missing, it will remain as missing, without imputation of missing value at this visit, which is similar to using Estimand E2a (treatment policy estimand). The same approach of including all observed data collected/assessed regardless of any prior intercurrent events will also be applicable to Part 2 OL Safety phase. Missing binary efficacy endpoints in Part 2 OL Safety phase will not be imputed as non-response, only observed values will be summarized.

In general, missing values in any (binary or continuous) efficacy endpoint will not be imputed when summarizing these endpoints using descriptive statistics. In addition, missing values for safety endpoints will not be imputed.

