6.2.5. Other Exploratory Continuous Endpoints (Repeated Visits)

For Part 1, continuous exploratory endpoints will be descriptively summarized by treatment group and by visits for percentage change from baseline in EASI score and change from baseline in POEM.

For Part 1 OLE, continuous exploratory endpoints at all visits from Week 20 up to Week 68 (eg, percent change from baseline in EASI score), will be analyzed using a single MMRM without imputation for missing data (Section 5.2.2.2). The model will include all data from Part 1 DB Week 4 up to Part 1 OLE Week 68 on the FAS (Appendix 3). The actual stratification factor (ie, baseline IGA of 3 or 4) from clinical database will be used in the MMRM analysis. This analysis will provide the LSM of the treatment groups by visit, the LSM of the treatment difference by visit (Etrasimod 2 mg QD versus Placebo → Etrasimod 2 mg QD from Week 20 to Week 68; results from Week 4 to Week 16 will not be displayed from this analysis since they will come from a repeated analysis of the Part 1 DB phase for this endpoint) in percent change from baseline in EASI score, 95% CI and the 2-sided p-value by visit (Section 5.2.2.2). This approach is also similary applied to change from baseline in

POEM including all data at Part 1 DB Week 16 (Etrasimod 2 mg QD versus Placebo), Part 1 OLE Weeks 32 and 68 (Etrasimod 2 mg QD versus Placebo → Etrasimod 2 mg QD) on the FAS. Results from all visits will be displayed.

For Part 2 OL Safety phase, continuous exploratory endpoints at all visits will only be descriptively summarized for the single treatment group of Etrasimod 2 mg QD using only observed values on the FAS (since intercurrent events are not considered in this Part 2 OL Safety phase). Therefore, missing values will not be imputed in this Part 2 OL Safety phase. This approach is applicable to percent change from baseline in EASI score and change from baseline in POEM score, at all visits from Week 4 to Week 52. The baseline is the pre-dose Day 1 of Part 2 OL Safety phase (Section 3.4).

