6.4.2. Study Conduct and Participant Disposition

Study conduct and participant disposition is summarized by frequency and percentages for the following sets by treatment group for Part 1 and Part 2.

- Total number of participants screened;
- Number of participants who failed screening;
- Number of participants randomized;
- Number of participants randomized and treated;
- Number of participants in the FAS;
- Number of participants in the FAS who discontinued from the study due to any reason (for Part 1 DB phase, this will be DB phase);
- Number of participants in the FAS who completed the study (for Part 1 DB phase, this will be DB phase);
- Number of participants in the SAS.

Participants who are treated but are not randomized will also be summarized if at least one participant falls into this category.

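### FAS and SAS are defined only through randomisation, so as written no Part 2 participant qualifies; separately, exploratory Part 2 summaries after Week 16 omit participants stopped at the EASI-50 check without saying so

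*SAP*

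**What the plan says.** **Analysis sets.** SAP 4.1: "The full analysis set (FAS) will include all participants who are randomized to the study". It then excludes anyone treated without being randomised. SAP 4.2 requires randomisation plus at least one dose, and adds "If a participant is treated but not randomized, then the participant will be excluded from SAS", with a narrative in the study report for each such case. Protocol 9.2 defines the safety set as "All participants randomly assigned to study intervention and who take at least 1 dose of study intervention" and the FAS likewise by random assignment; it has no separate exclusion sentence. Neither document defines another set for Part 2.

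**Where the sets are used.** SAP 4.2: "The SAS will be the analysis set for safety analyses in all phases of the study". SAP 3.1 and 3.5.1 make the safety endpoints primary for Part 2. SAP 6.2.4 and 6.2.5 place Part 2 efficacy on the FAS; the continuous endpoints, for example, are summarised "using only observed values on the FAS (since intercurrent events are not considered in this Part 2 OL Safety phase". SAP 6.5.6 uses the FAS for Part 2 protocol deviations. SAP 6.4.2 applies its disposition rows, two of which count randomised participants, to Part 2 as well, and adds: "Participants who are treated but are not randomized will also be summarized if at least one participant falls into this category".

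**How participants enter Part 2.** SAP 2.3: "approximately 340 additional (de novo) participants will be enrolled to receive etrasimod 2 mg orally, once daily". SAP 5.2 gives Part 2 a single treatment group.

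**Part 2 efficacy data.** SAP 5.3: "Missing binary efficacy endpoints in Part 2 OL Safety phase will not be imputed as non-response, only observed values will be summarized". Under SAP 5.2, descriptive rates use evaluable participants as the denominator. Protocol 7.1.5 stops study treatment in Part 2 for those below EASI-50 at Week 16, who then have only the early termination (ET) visit and safety follow-ups SFU 1 and SFU 2.

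**The concern.** The rule for who is in a set does not match where the set is used. Part 2 exists to supply long-term safety data, and its primary endpoints run on a set whose written definition no Part 2 participant meets. SAP 4 requires membership to be assessed and documented before the database is released, so someone will have to apply that definition. It also leaves open whether a person enrolled in Part 2 but never dosed counts in the FAS.

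The second matter is exploratory and touches no test or primary endpoint. Poor responders are removed at Week 16 by design, and later rates are computed only on those with data. A higher rate at Weeks 36 to 52 could then be read as improvement or maintenance when only the population has changed. The stopping rule itself is not questioned here.

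**Working it through.** **A. Set membership.** No arithmetic is involved, and Protocol 9.5 gives the 340 without a calculation, so there is no formula to reproduce. The texts side by side:

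| Source | Requirement or fact | Effect on a Part 2 participant |
|---|---|---|
| Protocol 9.2 | Both sets: randomly assigned | Not met |
| SAP 4.1 (FAS) | Randomised; treated-only excluded | Excluded |
| SAP 4.2 (SAS) | Randomised and dosed; treated-only excluded | Excluded |
| Protocol 1.3.1 (Part 1 schedule) | Has a Randomization row | Not applicable |
| Protocol 1.3.3 (Part 2 schedule) | No such row | No step that could meet the rule |

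The schedule notes confirm the difference: the Day 1 pregnancy test must precede randomisation in Part 1 but dosing in Part 2, and the ECG notes change in the same way.

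Literal result: 0 of about 340 in the FAS and 0 in the SAS. The sets can hold at most the 60 Part 1 participants out of 60 + 340 = 400 planned (15%). Every treated Part 2 participant would fall in the treated-but-not-randomised row of SAP 6.4.2.

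**B. Timing after a Week 16 stop in Part 2.** The plan's target-day rule is week × 7 + 1: Week 16 = 113, Week 24 = 169, Week 36 = 253, matching SAP Table 9. Inputs: Week 16 visit window ±5 days and SFU 2 at 4 weeks ±3 days after last dose (Protocol 1.3.3). Assumption: the last dose is on the visit day or the day before.

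- Week 16 visit: 113 ± 5 = Day 108 to 118.
- ET visit, within 1 week of last dose: at the latest 118 + 7 = Day 125.
- SFU 2, last dose on the visit day: 108 + 25 = Day 133 to 118 + 31 = Day 149. Last dose the day before: Day 132 to 148.
- Windows (SAP Table 9): Week 16 is Day 85–140, Week 24 is Day 141–210, and Week 36 opens at Day 211.
- Gap from the latest SFU 2 to the Week 36 window: 211 − 149 = 62 days.

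So no scheduled value from these participants reaches Weeks 36, 44 or 52. EASI, IGA and the two NRS scales are collected at SFU 2, but POEM is not. Their ET POEM (Day 125 or earlier) precedes the Week 24 window, so POEM at both Weeks 24 and 52 also lacks them.

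SFU 2 efficacy values do have a place: SAP Appendix 2.1 makes all visits eligible for windowing and SAP 5.3 includes all observed Part 2 data. Treating the 11 × 7 = 77 combinations of visit day and SFU 2 day as equally likely (an assumption), 42/77 = 54.5% fall at Day 141 or later with the last dose on the visit day, and 35/77 = 45.5% with it the day before. These enter Week 24; the rest enter Week 16.

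**C. Illustrative size.** If f is the fraction with data, observed-case rate ÷ rate with missing as non-response (MR=NR) = 1/f:

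| f | 0.5 | 0.6 | 0.7 | 0.8 | 0.9 |
|---|---|---|---|---|---|
| Ratio | 2.00 | 1.67 | 1.43 | 1.25 | 1.11 |

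Example in which nobody's response changes, with assumed inputs: 102 of 340 are EASI-75 responders at Week 16 (30%), and there is no loss other than the EASI-50 stop. Responders all pass EASI-50, so 102 remain. Observed-case rates at Weeks 36–52 are 102/170 = 60%, 102/238 = 42.9% and 102/306 = 33.3% if 50%, 70% and 90% pass. The MR=NR rate stays at 102/340 = 30%.

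At 70% passing, 340 − 238 = 102 are stopped. With their SFU 2 values windowed, Week 24 has N = 238 + 102 × 0.455 = 284 to 238 + 102 × 0.545 = 294, giving 35.9% to 34.7%. Without them it is 42.9%.

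**The case against.** **On the sets.** Nobody could mean to exclude all of Part 2: the SAP applies the SAS to every phase, names the FAS for Part 2 efficacy, and plans Part 2 adverse event tables (SAP 6.5.1). The exclusion is evidently aimed at stray cases. Protocol 6.3 speaks of a randomisation number without limiting it to Part 1, and Protocol 6.9.2, 8.3.9 and 8.3.10 use randomisation loosely for study entry. All of this stands as evidence of intent. A reader might infer that Part 2 safety data will be dropped or that the safety database is at risk; the documents do not support that. But the generic allocation text does not randomise a single-group part, and clear intent does not correct an explicit exclusion.

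**On the observed-case summaries.** They are a stated choice for exploratory single-arm data, the stopping rule is openly described, and n and N appear by visit (SAP 5.2), so a careful reader could rebuild the other rate. That stands, and is why this is only an improvement. Three stronger readings also fail:

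- That Week 24 handling is undefined. SAP 5.3 and Appendix 2.1 do place SFU 2 values.
- That an SFU 2 value always displaces the Week 16 value. The latest-observation rule in Appendix 2.1 covers people who leave the study early. Protocol 7.1 says stopping treatment is not study withdrawal, while Protocol 7.2 lists lack of efficacy among reasons for leaving the study. If the rule does not apply, the value nearest Day 113 is used, and SFU 2 is at least 132 − 113 = 19 days away.
- That every stopped participant is wholly absent later. Unscheduled assessments remain eligible.

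**Conclusion.** The analysis-set definitions are wrong as written and should be corrected before Part 2 participants are classified. Read literally, 0 of about 340 qualify for either set; this needs no assumption. The consequence is a mismatch between definition and use, not a prediction that data will be lost.

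The second part holds as an inexpensive improvement to exploratory summaries. Apart from unscheduled values, participants stopped at the Week 16 check are missing from observed-case summaries at Weeks 36, 44 and 52, and from POEM at Weeks 24 and 52. A rate can therefore rise with no change in anyone. Off-treatment SFU 2 values enter the Week 16 or Week 24 window, and whether they can replace the Week 16 value is ambiguous. The timing rests on the last dose falling on the Week 16 visit day or the day before. A reader might take the 30% to 43% example as an estimate of inflation; it is not. The documents give no EASI-50 or dropout rate for Part 2, so the true size cannot be computed.

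**What to change.** **Analysis sets.**

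- In Protocol 9.2 and SAP 4.1/4.2, define the Part 2 FAS as all enrolled participants and the Part 2 SAS as all enrolled participants with at least one dose.
- Limit the treated-but-not-randomised exclusion, its narrative and its disposition row to Part 1.
- In SAP 6.4.2, use *enrolled* and *enrolled and treated* rows for Part 2.

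**Exploratory Part 2 summaries.**

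- In SAP 5.3 and 6.2.4, keep the observed-case rates and add beside them an MR=NR rate over the Part 2 FAS, with the existing baseline ≥4 restriction for PP-NRS and Skin Pain NRS. Show both denominators.
- Label post-Week 16 observed-case summaries, including percent change in EASI and change in POEM in SAP 6.2.5, as being among participants continuing after the EASI-50 check.
- In SAP Appendix 2.1, state that SFU 2 efficacy values are shown under the nominal follow-up visit and not allocated to any Part 2 scheduled-visit window. The rule must cover every window: a stop at the Week 36 visit (Day 246–260, last dose that day) puts SFU 2 at Day 271–291, in the Week 36 or Week 44 window. Align the sentence in SAP 5.3 on using all observed data.

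**Cost.** Short wording changes, table labels, and one extra column per Part 2 binary endpoint. The MR=NR rates will look less favourable. They mean still on study and responding, not the rate had everyone continued. Leaving out SFU 2 values raises the Week 24 observed-case rate (in the example, from about 35–36% to 43%), so the two columns must be read together.

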5. GENERAL METHODOLOGY AND CONVENTIONS

For Part 1, there will be a total of 2 planned analyses. The first (interim) analysis (IA) for Part 1 will be conducted when all applicable participants have completed or discontinued from study prior to their Part 1 DB Week 16 visit. The IA will be performed by the Sponsor and it will include all efficacy and safety data through Week 16. Data summaries from the IA will be shared with the study team. The study team will review the data in the context of the overall benefit-risk profile of etrasimod for the treatment of moderate-to-severe AD with prior systemic failure. The efficacy and safety data up to Week 16 will be utilized to assess the primary efficacy endpoint, secondary efficacy endpoints, and safety endpoints (Section 2.2, Section 5.1) and to make a go/no-go decision for initiating Part 2 of the study, as well as for completing the 52-week treatment for the Part 1 participants in the OLE. The IA efficacy results through Week 16 for Part 1 DB phase is not final and definitive.

The second (final) analysis for Part 1 will be conducted when all applicable participants have completed or discontinued from study prior to their Week 68 visit (including safety follow-up visits at Weeks 70 and 72) if Part 1 OLE is planned for completion by the sponsor. Otherwise, if Part 1 OLE is decided to be terminated by the sponsor, the final analysis will only be conducted based on data collected up to the date of study termination. The final analysis will contain final safety and efficacy data, as Part 1 final database, to assess the primary endpoints, secondary endpoints as well as exploratory efficacy endpoints (Section 2.2). This will also include efficacy analyses for Part 1 DB phase repeated based on this final data, and this final analysis is considered final and definitive.

For Part 2, there will only be one final analysis when all applicable participants have completed their Part 2 OL Safety phase Week 52 visit (including safety follow-up visits at Weeks 54 and 56) if Part 2 OL Safety phase is planned by the sponsor based on the Part 1 DB IA result. The final analysis will contain final safety data to assess the primary safety endpoints, and final efficacy data to assess exploratory efficacy endpoints (Section 2.2).

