An interim analysis will be conducted after all Part 1 participants have completed the 16-week DB treatment period. The IA will be performed by the Sponsor and data summaries will be shared with the study team. The participants and investigators will remain blinded to the treatments the participants received for the placebo-controlled period. The study team will review the data in the context of the overall benefit-risk profile of etrasimod for the treatment of moderate-to-severe AD with prior systemic failure. The data review will include but is not limited to, efficacy measures of IGA and EASI-75 response and safety parameters including the incidence and severity of AEs, AESIs, and clinically relevant changes in ECG, and vital signs, and laboratory values. The efficacy and safety data will be utilized to make a go/no-go decision for initiating Part 2 of the study, as well as for completing the 52-week treatment for the Part 1 participants in the OLE. Once the decision is made it will be promptly communicated to the sites.

Part 2: If the IA results in a decision to proceed to Part 2 of the study, approximately 340 additional participants will be enrolled to receive etrasimod 2 mg orally, once daily, for 52 weeks in an open-label manner in order to fulfill the safety database requirements. Enrollment into Part 2 will not begin until the IA data from Part 1 are reviewed, and determination made as to the favorable benefit/risk of etrasimod 2 mg QD in this new target population. Non-responders, ie, participants not achieving at least EASI-50 will be discontinued at Week 16, Part 2.

The participant population in both Part 1 and Part 2 will include at least 40% of participants with moderate AD (IGA score of 3) and at least 40% of participants with severe AD (IGA score of 4). The application of topical emollients/moisturizers (including those containing ceramide, hyaluronic acid, or urea) will be required at least once daily for at least 1 week prior to baseline (Day 1) and throughout the treatment period without change (ie, type, frequency, application). TCS and other medicated topical treatments for AD must be discontinued at least 1 week prior to baseline (Day 1) and are not permitted in the

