9.4. Interim Analyses

An interim analysis will be conducted to assess efficacy and safety after all Part 1 participants complete the 16-week DB treatment period. The interim analysis results will be used for decisions regarding stopping for futility and internal program development. Study conduct, including Part 1 participant continuation in OLE, will continue while the data are prepared and analyzed for the IA. The Part 2 enrollment will not be triggered until after the IA shows an acceptable safety and efficacy of etrasimod 2 mg QD in the target population. Based on the IA results, the study may continue to enroll participants, or the study may be early terminated. Details on the IA will be provided in the SAP. The IA will be conducted by the Sponsor (refer to Section 4.1). Prior to this formal Part 1 DB IA, Sponsor may perform earlier unblinded interim analyses to inform internal decision-making regarding the development program. These earlier interim analyses will be conducted and reviewed by a limited number of team members independent of the study team. Details on these earlier unblinded interim analyses will be described in an unblinding operational plan.

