7. INTERIM ANALYSES

An interim analysis (IA) will be conducted by the Sponsor in an unblinded manner to assess efficacy and safety after all applicable Part 1 participants complete or discontinue from study prior to the 16-week DB treatment period. The IA results will be used for decisions regarding stopping for futility and internal program development. Study conduct, including Part 1 participant continuation in OLE, will continue while the data are prepared and analyzed for the IA. The Part 2 enrollment will not be triggered until after IA shows an acceptable safety and efficacy of etrasimod 2 mg QD in the target population. Based on the IA results, the study may continue, or the study may be terminated early.

Specifically, the scope of this IA includes the following. When all applicable Part 1 participants have completed the 16-week DB treatment phase, an interim datacut will be performed that will include all efficacy and safety data up to Week 16 visit. After data cleaning is performed, unblinding of Part 1 DB treatment assignments will take place, and interim database will be released for the IA to be performed by the Sponsor and the study team. Investigators and other site staff will remain blinded during the OLE to participants' treatment assignment received in the Part 1 DB phase until the end of Part 1 OLE. Efficacy data summary will include the assessment of primary efficacy endpoint, secondary efficacy endpoints, and exploratory efficacy endpoints for Part 1 DB (Section 2.2) using the prespecified statistical methodologies (Section 5) to perform all relevant analyses described for Part 1 DB including subgroup analysis (Section 6.3). Safety data summary will include the assessment of all relevant safety endpoints (Section 3.5) descriptively summarized up to end of Part 1 DB phase.

Prior to this formal Part 1 DB IA, Sponsor may perform earlier unblinded interim analyses to inform internal decision-making regarding the development program. These earlier interim analyses will be conducted and reviewed by a limited number of team members independent of the study team. Details on these earlier unblinded interim analyses will be described in an unblinding operational plan.

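### The interim safety outputs stop at Week 16, so open-label etrasimod safety data already collected are not in the specified package for the Part 2 and OLE decisions

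*SAP*

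**What the plan says.** **Trigger.** SAP 5 times the IA for "when all applicable participants have completed or discontinued from study prior to their Part 1 DB Week 16 visit".

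**Cut.** SAP 5 says that "it will include all efficacy and safety data through Week 16". SAP 7 agrees: "an interim datacut will be performed that will include all efficacy and safety data up to Week 16 visit", with safety "descriptively summarized up to end of Part 1 DB phase".

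**Use.** SAP 5 uses the data up to Week 16 "to make a go/no-go decision for initiating Part 2 of the study, as well as for completing the 52-week treatment". Protocol 4.1 likewise uses the interim efficacy and safety data for starting Part 2, "as well as for completing the 52-week treatment for the Part 1 participants in the OLE".

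**Meanwhile.** Both arms move to open-label etrasimod 2 mg at Week 16 (SAP 5.2). Protocol 9.4 adds: "Study conduct, including Part 1 participant continuation in OLE, will continue while the data are prepared and analyzed for the IA".

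**Switch day.** SAP Appendix 2.1, Table 8, footnote b keeps all data from the day of the first open-label dose in Week 16 or earlier, except AEs. AEs starting that day go to Week 20 or later.

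**Next look at OLE data.** SAP 5 plans two analyses for Part 1. OLE data first enter a planned output at the second, final one.

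**The concern.** Long-term safety in the OLE is a primary objective. Yet the outputs specified for deciding whether to complete the OLE, and whether to open 52 weeks of treatment to a further group of about 340, contain no OLE safety data. In those outputs, treatment on etrasimod means about 30 people for up to 16 weeks.

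Former placebo participants add up to 30 people newly exposed to etrasimod. AEs starting on their first etrasimod day fall outside the cut under footnote b. Their post-dose vital signs and ECG from that visit fall inside it, but SAP 5.2 labels all visits up to Week 16 by randomized group, so these on-etrasimod measurements would be shown under Placebo. A reader of the IA tables would then miss the first-dose AEs of this group and could misread its first-dose heart-rate and ECG findings as placebo findings.

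**Working it through.** **The plan's own figures.** No exposure figure is given. The only design calculation is the precision in Protocol 9.5, and it reproduces with 30 per arm and rates of 9% and 39%: 1.96 × √(0.09 × 0.91/30) = 10.2% and 1.96 × √(0.39 × 0.61/30) = 17.45%, both at most 17.5%; for the difference, 1.96 × √(0.09 × 0.91/30 + 0.39 × 0.61/30) = 20.24%, against 20.2% stated. It concerns efficacy only.

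**Inputs for exposure.** From the documents: 60 participants randomized 1:1, 16 weeks of DB treatment, both arms on etrasimod afterwards, OLE of 52 weeks. Not stated, so assumed: accrual duration A (weeks), accrual shape, share c entering the OLE, dropout, and any lag to the cut.

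**DB etrasimod exposure.** 30 × 16 = 480 participant-weeks.

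**OLE exposure when the last participant reaches Week 16.** 60 × c × mean time since own Week 16.

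- Uniform accrual (A up to 52): the mean time is A/2. With c = 1, OLE exposure is 30A and the omitted share is 30A/(30A + 480) = A/(A + 16).
- Accrual rate rising linearly from zero: the mean time is A/3, so OLE exposure is 20 × c × A.

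| Scenario | OLE participant-weeks | Omitted share |
|---|---|---|
| Uniform, c = 1, A = 8 | 240 | 33% |
| Uniform, c = 1, A = 12 | 360 | 43% |
| Uniform, c = 1, A = 26 | 780 | 62% |
| Uniform, c = 1, A = 52 | 1560 | 76% |
| Ramp, c = 0.75, A = 26 | 390 | 45% |
| Ramp, c = 0.90, A = 26 | 468 | 49% |

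Adding 85% of full DB exposure (408 participant-weeks), 70% OLE entry and 30% stopping at OLE week 16, the share at A = 26 is 56% (uniform) or 47% (ramp). In the uniform base case one half is passed only when A exceeds 16 weeks.

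**Effect of a later cut.** If safety were cut 6 weeks after the last Week 16 visit, the uniform mean becomes A/2 + 6. At A = 12 with c = 1 this is 60 × 12 = 720 participant-weeks, or 720/1200 = 60% of exposure beyond the DB period.

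**People exposed.** With zero events of a given type, the exact one-sided 95% upper bound on risk is 1 − 0.05^(1/n). It is 9.5% for n = 30 and 4.9% for n = 60 (every placebo participant switching).

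**The case against.** The case on the other side has real content.

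- **OLE safety is watched.** The E-DMC monitors throughout (Protocol 10.1.5.1), SAEs reach the sponsor within 24 hours (Protocol 8.4.1.1), and AESIs are followed close to real time with regular aggregate analyses (Protocol 8.4.8). A reader might infer that the plan ignores OLE safety, and the documents do not support that. What stands is narrower: nothing routes this information into the go/no-go review.
- **The review list is open.** Protocol 4.1 and SAP 2.3 say the review is not confined to the listed measures. That permits additions and does not bar OLE data, but it concerns measures rather than time and specifies no OLE output.
- **There is other evidence.** A reader might infer that the decision rests only on 16-week data from 30 people. SAP 5 calls for review against etrasimod's overall benefit-risk profile, and the protocol cites a completed 52-week OLE in AD, long-term alopecia areata data and the Phase 3 UC program (Protocol 2.3, 2.3.3). The limit applies to this trial's specified outputs.
- **First-dose data are not all lost.** A reader might infer that the placebo group's first-dose reactions are missing altogether. Footnote b keeps that day's vital signs and ECG; only AEs starting that day move out.
- **OLE data have no concurrent control.** True. The Week 16 cut isolates the only controlled safety comparison and should be kept. The addition is descriptive.

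**Conclusion.** The point holds as a gap in what the IA is specified to show. The Week 16 cut, its use for both decisions and the continuing OLE are explicit, so some open-label data will exist at the IA and lie outside its planned tables unless accrual is almost instantaneous.

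The size is uncertain. The omitted share of etrasimod exposure runs from about 33% to 76% as uniform accrual goes from 8 to 52 weeks with full uptake and no lag, and is about 45-49% with ramped accrual over 26 weeks and 75-90% OLE entry. A reader might infer that more than half is omitted. That holds under slower accrual but cannot be asserted, because no accrual period or OLE uptake is given. The gap does not depend on passing one half.

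This is a cheap improvement. It does not affect the validity of the Week 16 efficacy or safety comparison.

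**What to change.** In SAP 5 and SAP 7:

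1. Keep the Week 16 cut for efficacy and for the controlled DB safety comparison.
2. Add a descriptive cumulative Part 1 DB+OLE safety summary to a stated calendar cut-off date, covering TEAEs, SAEs, AESIs, discontinuations, laboratory values, ECG and vital signs.
3. Present it by treatment taken at onset or measurement, with etrasimod exposure time, so that switch-day AEs and Week 16 post-dose measurements in former placebo participants count as on etrasimod.
4. State that the go/no-go review uses this summary.

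**Cost.** Some extra data cleaning and tables at the IA. SAP 6.5.1 already specifies TEAE displays for Part 1 DB+OLE, so part of the programming is planned. OLE treatment is open-label and the study team is unblinded to DB assignments for the IA anyway (Protocol 6.4.3), so no further unblinding is needed; sites and participants stay blinded to DB assignment as now planned. The added data have no concurrent control and should be labelled so.
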